8.2.2.4 Objective response rate (ORR)

ORR will be described overall and by subgroup defined in section 5.3.

Participants who do not have a post-baseline radiographic tumor assessment due to early progression, who receive anti-tumor therapies other than the study treatments prior to reaching a CR or PR, or who die, progress, or drop out for any reason prior to reaching a CR or PR will be counted as non-responders in the assessment of OR. Each participant will have an objective response status (0: no OR; 1: OR). OR rate (ORR) is the proportion of participants with OR in the FAS.

ORR will be calculated along with the 2-sided 95% CI using the Clopper-Pearson method (exact CI for a binomial proportion as computed by default by the FREQ procedure using the EXACT option).

ORR will also be described by subgroup (See section 5.3 for subgroup definition).

8.2.2.5 Duration of response (DOR)

For DOR, endpoint will be analyzed using a survival analysis, in the FAS, using the following table for censorship, and date of first response (Complete Response or Partial Response) as starting date.

Table 4: Event Date and Outcome for DORs

Scenario	Date of Event/Censoring	Outcome
Tumor assessment with a reported progressive disease, after response was observed.	Progression Date	Event
Death (whatever the cause) without treatment discontinuation	Death Date	Event
No reported progressive disease during the study nor death.	Last News Date	Censored
Lost to follow-up or early study discontinuation without stopping treatment	Last News Date	Censored
Treatment discontinuation	Discontinuation Date	Censored

DOR will also be described by subgroup (See section 5.3 for subgroup definition).

8.2.2.6 Duration of treatment (DOT)

DOT will be analyzed using a survival analysis, in the FAS, using the following table for censorship, and date of first study treatment intake as starting date.

Table 5: Event Date and Outcome for DOTs

Scenario	Date of Event/Censoring	Outcome
Permanent Treatment discontinuation	Discontinuation Date	Event
Death (whatever the cause)	Death Date	Event
No permanent discontinuation reported at the end of the study	Last News Date	Censored
Lost to follow-up or early permanent study discontinuation without stopping treatment	Last News Date	Censored

DOT will also be described by subgroup (See section 5.3 for subgroup definition).

8.2.2.7 Patterns of progression under avelumab

Progression under avelumab will be described:

- Progression of known lesions, target, or non-target (Yes/No)
 - If 'No', description of the site for the new lesions.

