## 8. RESEARCH QUESTION AND OBJECTIVES

The study will generate clinical data on the characteristics of adv/mUC patients treated with avelumab and on the effectiveness and safety of avelumab in the real-world setting.

Primary objective: to estimate Overall Survival (OS) of adv/mUC patients treated with avelumab in the real-world setting.

Secondary objectives :

- To describe patients' characteristics: ECOG (0-4) at ChT 1st and avelumab initiation, sex, age, ChT regimens received in 1st line (Cis/Gem, Carbo/Gem, Cis/Carbo/Gem, MVAC regimens, others), median number of ChT cycles received in 1st line, median time between the end of ChT 1st line and the start of avelumab, best response to 1st line chemotherapy (CR, PR, SD; CR-RP, SD), site and histology of the primary tumor (bladder, urethra or upper tract), site of baseline metastasis before ChT and avelumab (visceral vs non visceral), biological abnormalities (neutropenia, lymphopenia, impaired renal function, anemia), PD-L1 status and FGFR abnormality, Bajorin risk classification (0, 1, 2) evaluated before the start of ChT 1st line, use of concomitant

treatments (corticosteroids/anti-inflammatory steroids (AIS)/non-steroidal anti-inflammatory drugs (NSAIDs), angiotensin-II-receptor antagonists (sartans)/angiotensin-converting enzyme (ACE) inhibitors, antibiotics, proton pump inhibitors (PPI)) at avelumab initiation, type of neoadjuvant and adjuvant treatments.

- To estimate: Overall Survival from the start of ChT in 1st line, Progression Free Survival one and two (PFS1 and PFS2). Overall Response Rate (ORR), Duration Of Response (DOR) and Duration Of Treatment (DOT) while receiving avelumab.
- To describe the pattern of progression while receiving avelumab.
- To describe subsequent treatments and response to these treatments.
- To describe the safety profile of avelumab.
- To describe use of premedication (acetaminophen and antihistamine).
- To describe Patient-Reported Outcomes (PROs) related to symptoms via the NCCN/FACT FBISI-18 questionnaire and related to global health via the EQ-5D-5L questionnaire. This objective will be evaluated only among patients initiating avelumab after the start of the study.

The primary and secondary objectives will be evaluated on the overall population and for prespecified subgroups.

- Main subgroup of interest: histology (UC with variant; UC without variant).

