### 9.1.2. Secondary endpoints

- OS from the start of the chemotherapy used in 1st line: time between the first injection of the chemotherapy used in 1st line and the date of death from any cause.
- PFS1: time between the first injection of avelumab and the date of progression or death from any cause. Progression status will be defined according to RECIST 1.1.
- PFS2: time between the first injection of avelumab and the date of progression or death from any cause during the 2nd line of treatment post-avelumab. Progression status will be defined according to RECIST 1.1.
- ORR: proportion of patients with a Complete Response or Partial Response as a best response during the avelumab treatment. Responses to treatment will be defined according to RECIST 1.1.
- DOR: time between the beginning of the response and progression or death from any cause.
- DOT: time between the first and last dose of avelumab.
- Patterns of progression under avelumab: metastatic sites and type of progression (new lesion(s)/progression of known lesion(s)).
- Subsequent treatments and response to these treatments: DOT, PFS, ORR and OS.
- Safety: AEs of any type, grade 3-4 AEs, AEs leading to interruption or discontinuation, AEs leading to death.

090177e1a41aac13\Final\Final On: 28-Jul-2025 13:50 (GMT)

- Premedications (acetaminophen and antihistamine): Proportion of patients who received a premedication at each injection of avelumab. Median number of cycles with premedication. To evaluate the correlation between infusion-related reactions and premedication.
- Evolution of PROs NCCN/FACT FBISI-18 and EQ-5D-5L scores during avelumab treatment.

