Clinical Follow-up data	
 
• Avelumab administration               
 
. Date of each infusion, dose
 
. Use of premedication (acetaminophen and antihistamine)
 
 
 
• Tumoral response under avelumab               
 
. At inclusion (for retrospective data collection): tumoral evaluation (yes/no), best response since avelumab initiation, date of partial or complete response if so, date of progression if so with site(s) of progression and type (new or preexisting lesions).
 
. Tumoral evaluation since last visit (yes/no, date), response (partial remission, complete remission, progression, stable disease, not evaluable), site(s) of progression if so and type (new or preexisting lesions).
 
 
 
• ECOG if the patient is still on avelumab
 
• Avelumab discontinuation
 
	X		X

090177e1a41aac13\Final\Final On: 28-Jul-2025 13:50 (GMT)

	
 
. Temporary interruption(s) with reason and dates
 
. Permanent discontinuation with reason and date
 
• Subsequent treatments after avelumab discontinuation
 
. Regimen and dates start/discontinuation
 
. Best response, progression with date,
 
• Death with date and cause
 
• Lost to follow-up if so and date
 
• Date of withdrawal if so
 
			
Safety	Adverse events (see section 11)	X		X
Concomitant treatments	Corticosteroids/AIS/NSAIDs, sartans/ACE inhibitors, antibiotics, PPI, if the patient is still on avelumab	X		X
Patient reported outcome (PRO)	
Patients initiating avelumab after the start of the study will complete NCCN/FACT FBISI-18 and EQ-5D-5L questionnaires:
 
 
1) at the time of avelumab initiation (baseline)
 
2) at different time points after initiation if the patient is still treated with avelumab : 6 weeks, 3 months, every three months for up to 2 years, tumor progression if so
 
3) at avelumab discontinuation (whatever the reason is)
 
	X	X	X

\* In order to validate the type of variants, anonymized anatomical pathology reports of the patients concerned will be collected and reviewed by the steering committee.

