4.2 STATISTICAL DECISION RULES

All the analyses will be purely descriptive. Two-sided 95% confidence interval will be provided for estimates of primary interest.

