6 ENDPOINTS AND COVARIATES

6.1 EFFICACY/EFFECTIVENESS ENDPOINT(S)

6.1.1 Time-to-event endpoints

Variable	Role	Data source(s)	Operational definition
Overall Survival (OS)	Time to Event Outcome (primary endpoint)	Patient medical records and CRF	Time (month) from the first injection of avelumab to death, whatever the reason +1
Overall Survival 2	Time to Event Outcome (secondary endpoint)	Patient medical records and CRF	Time (month) from the first injection of the chemotherapy used in 1st line to death, whatever the reason +1
Progression Free Survival (PFS)	Time to Event Outcome (secondary endpoint)	Patient medical records and CRF	Time (month) from the first injection of avelumab to the date of progression or death from any cause +1.
Progression Free Survival (PFS) 2	Time to Event Outcome (secondary endpoint)	Patient medical records and CRF	Time (month) from the first injection of avelumab to the date of progression or death from any cause during the 2nd line of treatment post-avelumab +1.
Objective Response Rate (ORR)	Outcome (secondary endpoint)	Patient medical records and CRF	Proportion of patients with a Complete Response (CR) or Partial Response (PR) as a best response during the avelumab treatment.
Duration Of Response uber avelumab (DOR)	Time to Event Outcome (secondary endpoint)	Patient medical records and CRF	Time (month) from the beginning of the response to progression or death from any cause + 1.
Duration Of	Time to Event	Patient medical	Time (month) from the first to last dose of avelumab + 1.

PFIZER CONFIDENTIAL

CT24-WI-GL03-RF02 2.0 Non-Interventional Statistical Analysis Plan For Primary Data Collection Study

01-Jun-2020

Page 12 of 28

Treatment (DOT)	Exposure	records and CRF	
Patterns of progression under avelumab	Outcome (secondary endpoint)	Patient medical records and CRF	Description of metastatic sites and type of progression (new lesion(s)/progression of known lesion(s)).
OS of subsequent treatment	Time to Event Outcome (secondary endpoint)	Patient medical records and CRF	Time (month) from the first injection of avelumab-subsequent treatment to death, whatever the reason +1

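### SAP 8.2.2.7 describes new-lesion sites only when known lesions did not progress, and no sites otherwise, which is narrower than the endpoint defined in SAP 6.1.1 and protocol 9.1.2

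*SAP*

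**What the plan says.** The protocol sets a secondary objective in section 8: "To describe the pattern of progression while receiving avelumab". Section 9.1.2 defines the matching endpoint: "Patterns of progression under avelumab: metastatic sites and type of progression (new lesion(s)/progression of known lesion(s". Table 2 in section 9.3 lists the follow-up data to be collected for it: "site(s) of progression if so and type (new or preexisting lesions". It lists similar items at inclusion for the retrospective period.

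SAP 6.1.1 repeats the protocol definition: "Description of metastatic sites and type of progression (new lesion(s)/progression of known lesion(s". Neither definition limits the sites to one type of progression.

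The analysis rule is in SAP 8.2.2.7. It has a single top-level item, "Progression of known lesions, target, or non-target (Yes/No", and a single branch beneath it, which applies when the answer is 'No' and asks for "description of the site for the new lesions". It gives no branch for 'Yes' and has no separate item for the presence of new lesions.

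The summary of analyses in SAP 8.2.5 adds only that the progression description uses the FAS and descriptive statistics. SAP 8.2 requires every analysis at least overall and by histological status, so the same rule also feeds the comparison by histology.

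**The concern.** Progression of known lesions and the appearance of new lesions can occur in the same patient. The rule in 8.2.2.7 treats them as alternatives, because new lesions enter the description only once known-lesion progression has been ruled out.

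The site distribution it produces would describe patients with new lesions alone, yet a reader would probably take it as describing new lesions under avelumab in general. The omission would be systematic, since it depends on how the patient progressed. Sites of progression in known lesions, which the endpoint definition also covers, would not be tabulated under this rule. For a descriptive objective the table is the whole result, so a gap in the table is a gap in the answer.

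**Working it through.** The plan states no figure here to reproduce. The check is logical: pass each possible pattern of progression through the rule and compare the output with the definition in SAP 6.1.1 and protocol 9.1.2.

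| Pattern | Answer to the known-lesion item | Output under SAP 8.2.2.7 | Required by SAP 6.1.1 and protocol 9.1.2 |
|---|---|---|---|
| (a) Known lesions only | Yes | Type recorded as known-lesion progression; no site | Type and sites |
| (b) New lesions only | No | New-lesion sites | Type and sites |
| (c) Both | Yes | Same as (a): no new-lesion indicator, no site | Both types and their sites |

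Three results follow from the table.

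1. Patients in (c) are left out of the new-site description.
2. Patients in (c) cannot be told apart from those in (a), so the number with any new lesion is not obtained. The count of 'No' answers gives only (b).
3. No site is described for known-lesion progression in (a) or (c).

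**Size of the first result.** Let *n* be the number of patients with new lesions only and *b* the number with both. The share of patients with new lesions who are left out of the site description is *b* / (*n* + *b*). The documents give neither *n* nor *b*. The share is simply the overlap itself: if 10% of patients with new lesions also progressed in known lesions, 10% are left out, and if 50% did, 50% are left out. Both percentages are assumptions chosen to show a range. The third result needs no assumption about overlap, because it affects every patient whose answer is 'Yes'.

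**Whether another section repairs the rule.** SAP 8.2.5 names the output without specifying its content. SAP 9 refers to a separate spreadsheet for the list of tables and shells, which is not among the documents. SAP 6.1.1 defines the endpoint in full but does not say how to tabulate it. None of these overrides the nested rule in 8.2.2.7.

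**The case against.** The strongest reply is that the SAP is not silent on sites. Section 6.1.1 carries the full definition, and a programmer working from it, or from table shells not available here, might produce sites for every progressor. This stands as a limit. A reader might infer that the SAP nowhere provides for sites of known-lesion progression, and 6.1.1 shows that this goes too far. The defect is an inconsistency within the SAP, with 8.2.2.7 narrower than 6.1.1, and the loss of output is a risk that depends on how the table is programmed.

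A second reply concerns data capture. A reader might infer that both types are already recorded and that rewording the SAP is enough. The documents do not establish this. The CRF is listed in protocol Annex 1 as a stand-alone document and is not provided, and Table 2 joins the two lesion types with 'or'. If the field accepts only one type, pattern (c) is lost at data entry and no analysis rule can recover it.

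A third reply is that the consequence is modest. SAP 4.2 states: "All the analyses will be purely descriptive". The rule still reports known-lesion progression, and it reports new sites for patients with new lesions only. One might be tempted to say that the objective is answered wrongly, or that the patients left out are those with the most extensive disease. The first overstates an incomplete table, and nothing in the documents equates progression in both ways with extent of disease.

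These replies narrow the point but do not remove it. The written rule still contradicts the definition it is meant to carry out.

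**Conclusion.** The point holds as an inconsistency to correct before the final analysis. As written, SAP 8.2.2.7 is narrower than the endpoint defined in SAP 6.1.1 and protocol 9.1.2. If it is followed literally, the description of progression patterns will be selectively incomplete: new sites missing for patients who progressed in both ways, those patients merged with known-only progressors, and no sites for known-lesion progression.

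The number of patients affected cannot be stated from the documents. The conclusion assumes that the table is programmed as 8.2.2.7 is worded. The part about patients with both types also assumes that the CRF can record both for one progression. The gap in sites for known-lesion progression does not depend on that second assumption.

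The effect is confined to one descriptive secondary endpoint, overall and by histology. OS, PFS and the sample size are unaffected.

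**What to change.** First, confirm whether the CRF lets both lesion types be recorded for the same progression, and whether sites are linked to lesion type.

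- **If both types can be recorded:** replace the nested rule in SAP 8.2.2.7 with two independent indicators, progression of known lesions (yes/no) and new lesions (yes/no). Cross-classify progressors as known only, new only or both. Tabulate sites of progression for all progressors, by lesion type where the data allow.
- **If only one type can be recorded:** tabulate sites for all progressors and state in the SAP and the report that the combined pattern cannot be identified.

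In either case, align the table shell with SAP 6.1.1. The cost is a change of SAP wording, one table and a check of the CRF. The first option needs no data beyond what protocol Table 2 already lists, provided the CRF check is satisfactory.

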8.2.2.8 OS of subsequent treatment

For OS of subsequent treatment, endpoint will be analyzed thanks to survival analysis method, using the same censorship as for primary criterion (Table 1). The analysis will be

PFIZER CONFIDENTIAL

CT24-WI-GL03-RF02 2.0 Non-Interventional Statistical Analysis Plan For Primary Data Collection Study

01-Jun-2020

Page 20 of 28

made in the FAS for participants receiving at least one dose of subsequent treatment. The starting date to be used is the date of first intake of subsequent treatment.

The subsequent treatment is defined as the line of treatment following the maintenance with avelumab.

8.2.2.9 PFS of subsequent treatment

For PFS of subsequent treatment, endpoint will be analyzed using survival analysis method, in the FAS for participants receiving at least one dose of subsequent treatment, using the following table for censorship, and date of first intake of subsequent treatment starting date.

Table 6: Event Date and Outcome for PFSs

Scenario	Date of Event/Censoring	Outcome
Progression recorded before discontinuation of subsequent treatment (and after initiation)	Progression date	Event
Death (without any previous recorded progression of disease)	Death Date	Event
Final discontinuation of subsequent treatment during the study before any progression or death	Treatment Discontinuation Date	Censored
Lost to follow-up or early study discontinuation without progression or death	Last News Date	Censored

8.2.2.10 ORR of subsequent treatment

ORR will be described and analyzed according to the specifications mentioned in section [8.2.2.4](#).

8.2.2.11 DOT of subsequent treatment

For DOT, endpoint will be analyzed using survival analysis, in the FAS, using the following table for censorship, and date of first intake of subsequent treatment starting date.

Table 7: Event Date and Outcome for DOTs

Scenario	Date of Event/Censoring	Outcome
Treatment discontinuation	Discontinuation Date	Event
Death (whatever the cause)	Death Date	Event
No discontinuation reported at the end of the study	Last News Date	Censored

PFIZER CONFIDENTIAL

CT24-WI-GL03-RF02 2.0 *Non-Interventional Statistical Analysis Plan For Primary Data Collection Study*

01-Jun-2020

Page 21 of 28

Lost to follow-up or early study discontinuation without stopping treatment	Last News Date	Censored
---	----------------	----------

8.2.2.12 FBISI-18 score

Scores will be described at the following timepoint:

- Avelumab initiation (baseline)
- After initiation if the participant is still treated with avelumab:
 - o 6 weeks,
 - o 3 months,
 - o Every three months for up to 2 years,
 - o Tumor progression if so,
- Avelumab discontinuation (whatever the reason is).

The FBISI-18 score will be analyzed using a MMRM based on the windowing defined in section [11.1.1](#).

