#### Follow-up:

[figure not shown]
The last patient prospectively included will be followed for 2 years. All other patients will be followed until death or until the end of the follow-up of the last patient prospectively included.

Patients who started avelumab before the start of the study will be followed retrospectively, but also prospectively for those still alive at the beginning of the study.

Follow-up visits will be made during the course of regular visits and/or hospitalisations. No additional visits or examinations are required by the protocol, as the study is observational: follow-up and treatment modalities will be at the sole discretion of the participating physician. Clinical data will be collected every three months after the inclusion in the study and until death or the end of the study: 24 months after the inclusion of the last prospective patient. Patients initiating avelumab after the start of the study (prospective part of the study) will complete PRO questionnaires : 1) at the time of avelumab initiation, 2) at different time points after initiation if the patient is still treated with avelumab (6 weeks, 3 months, and every three months for up to 2 years, tumor progression if so), 3) and at avelumab discontinuation.

Number of sites: the study will be proposed to all sites participating to the ATU program, plus some additional centers expected to treat patients after the ATU period. Approximately 100 sites are expected to participate to the study.

Figure 1. Study design

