### 9.7. Data analysis

A detailed statistical analysis plan will be available before the database lock.

All effectiveness analyses (except PRO analysis) will be performed on a Full Analysis Set (FAS) defined as all enrolled patients who received at least one injection of avelumab. "Enrolled" means a participant's, or his or her legally authorized representative's, agreement to participate in a clinical study following completion of the informed consent/assent process and who meet all eligibility criteria. Potential participants who are screened for the purpose of determining eligibility for the study, but do not participate in the study, are not considered enrolled.

The primary end point is the Overall Survival (OS). OS is defined as the time from the date of first injection of avelumab to the date of death due to any cause. Patients last known to be alive will be censored at date of last contact. OS will be summarized using the Kaplan-Meier method and displayed graphically. Confidence intervals (CIs) for the 25th, 50th (median) and 75th percentiles will be reported. In particular, six-months and one-year survival rate will be assessed with a 95%CI.

A first interim analysis (IA) will be performed 6 months after the inclusion of the 1st patient and then every year for publication purposes.

The data collected in the present study may also be analyzed together with data from other countries, to increase sample size to address with a higher precision some of the study objectives. The details of this pooled analysis will be described in a separate analysis plan.

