- Time-to-event endpoints will include the observation period before an event of interest or till the censoring date and therefore will be analysed on all participants included in the analysis set.

- Continuous longitudinal data will be analysed using a mixed model for repeated measures. Maximum likelihood estimates will be provided on all participants included in the analysis set without any imputation.

Missing dates or partially missing dates will be imputed conservatively for adverse events and prior/concomitant medications/procedures. Specific rules for handling of missing or partially missing dates for date of birth, adverse events, prior/concomitant medications/procedures, and diagnosis of urothelial carcinoma are provided in [11.1](#)

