8.1.4 Analysis of continuous longitudinal data

Changes from baseline at specified follow-up assessment time points will be analyzed using a mixed model for repeated measures (MMRM) under the MAR framework. Analyses will include the fixed, categorical visit (including baseline). An unstructured (co)variance structure will be used to model the within-participant errors. If this analysis fails to converge, the following structures will be tested: a heterogeneous Toeplitz covariance structure followed by the heterogeneous first-order autoregressive covariance structure will be considered. The covariance structure converging to the best fit, as determined by Akaike's information criterion, will be used as the primary analysis. The Kenward-Roger approximation will be used to estimate de-nominator degrees of freedom. Mean changes from baseline will be assessed using appropriate contrasts of least-squares means. Two-sided 95% confidence intervals will be provided.

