11 APPENDICES

11.1 APPENDIX 1: DATA DERIVATION DETAILS

11.1.1 Definition and use of visit windows in reporting

Data will be summarized in tables by visit (timepoint) when applicable. The following visit label and visit windows will be applied for all PRO endpoints:

Visit Label	Target Day	Visit Window
Baseline	1	Day 1 or before
Week 6	42	Day 2 to Day 66
Month 3	91	Day 67 to Day 137
Month 6	183	Day 138 to Day 228
Month 9	274	Day 229 to Day 320
Month 12	365	Day 321 to Day 410
Month 15	456	Day 411 to Day 501
Month 18	548	Day 502 to Day 593
Month 21	639	Day 594 to Day 684
Month 24	730	Day 685 to Day 775

In case of multiple observations falling within a given window, the observations selected for analysis will be identified as follows:

1. The observation closest to the target day will be used.
2. If the observations are at equal distance from the target day in absolute value, the one with a correct nominal visit label will be used.

PFIZER CONFIDENTIAL

CT24-WI-GL03-RF02 2.0 Non-Interventional Statistical Analysis Plan For Primary Data Collection Study

01-Jun-2020

Page 26 of 28

3. If neither (1) nor (2) can be used to identify the observation windowing, then the latest observation within the analysis window will be used.

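### By-visit absolute PRO means and the MAR mixed model can hide a decline because forms stop with avelumab; the planned change from baseline does not share the upward artefact

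*SAP*

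**What the plan says.** **Collection.** Protocol 9.1 (Follow-up) gives forms at avelumab start and then "if the patient is still treated with avelumab (6 weeks, 3 months, and every three months for up to 2 years, tumor progression if so", with a last form at discontinuation. SAP 8.2.2.12 repeats this: scheduled forms apply "After initiation if the participant is still treated with avelumab", and the final timepoint is "Avelumab discontinuation (whatever the reason is". None is planned after that. Only patients who start avelumab after study start receive forms (protocol 8; SAP 2.2).

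**Endpoint.** Protocol 9.1.2: "Evolution of PROs NCCN/FACT FBISI-18 and EQ-5D-5L scores during avelumab treatment".

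**Analysis.** SAP 6.1.1 defines each PRO outcome as an absolute value and a relative change from baseline at the available timepoints. SAP 11.1.1 supplies day windows from Baseline to Month 24: "The following visit label and visit windows will be applied for all PRO endpoints". None is labelled for progression or discontinuation. SAP 8.1.4 says change from baseline "will be analyzed using a mixed model for repeated measures (MMRM) under the MAR framework"; categorical visit is the only fixed effect it names. SAP 7 adds: "Maximum likelihood estimates will be provided on all participants included in the analysis set without any imputation".

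**Analysis set.** SAP 8.2.5 lists all three PRO scores under FAS. Protocol 9.7 says otherwise: "All effectiveness analyses (except PRO analysis) will be performed on a Full Analysis Set (FAS"). SAP 5 defines only the FAS and the safety set.

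**The concern.** The patients contributing a Month 12 or Month 24 score are those who stayed on avelumab. If patients who feel worse stop sooner, the remaining group had better scores from the outset. A by-visit absolute mean then compares a favourable remnant with the whole cohort at baseline.

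The mixed model has a different difficulty. Under MAR it fills in, implicitly, the scores that stopped or deceased patients would have had if they had stayed on drug and under observation. That is a hypothetical mean, whereas the protocol's endpoint is evolution while on avelumab. The SAP does not say which quantity it intends, how stopping or death enters, or whether the result is sensitive to MAR.

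The study has no comparator arm to expose selection, and analyses are repeated yearly for publication. The risk is that stable or improving symptoms are reported on maintenance treatment while the measured patients are getting worse.

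**Working it through.** **No plan figure to reproduce.** The documents give no sample size, effect or precision for the PRO endpoints. The only usable figure is the survival model in protocol 9.5, S(t) = exp(-t/29).

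**Step 1: who is left at Month 24.**
- Alive under the planning model: exp(-24/29) = 0.437. The Month 24 model mean would therefore extend to a cohort of which 56% have died.
- On avelumab: no duration is given. Assuming an exponential with median M, the share is 0.5^(24/M): 1.6% (M = 4 months), 6% (6), 16% (9), 25% (12).

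**Step 2: simulation. All inputs are assumptions.** Scale 0 to 72 (18 items x 4), higher = better as in SAP 6.1.3. True baseline mean 50, between-patient SD 9. Every patient flat or falling, with slopes of minus an exponential variable. Measurement SD 4 or 7. Stopping hazard = (ln 2/M) x exp(b x (50 - current score)/9), with M = 6 or 12 months and b = 0.5 or 1.0, so the hazard ratio per SD worse is exp(0.5) = 1.6 or exp(1.0) = 2.7. Forms are kept only on treatment, with or without a discontinuation form placed in the next window. The mixed model is the maximum-likelihood mean with unstructured covariance and visit as the only effect.

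Month 24 results for M = 6 and hazard ratio 2.7 (baseline mean 50):

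| Mean slope per month | Meas. SD | Discontinuation form used | Visit mean | Paired change, those assessed | Mixed-model change | True change, all patients |
|---|---|---|---|---|---|---|
| -0.02 | 4 | no | 59.6 | -0.3 | +0.7 | -0.5 |
| -0.02 | 7 | no | 59.2 | -0.5 | +2.2 | -0.5 |
| -0.02 | 4 | yes | 59.0 | -0.5 | +0.35 | -0.5 |
| -0.02 | 7 | yes | 58.8 | -0.4 | +1.7 | -0.5 |
| -0.2 | 4 | no | 57.7 | -3.1 | -2.2 | -4.8 |
| -0.2 | 7 | no | 57.5 | -2.9 | -0.5 | -4.8 |
| -0.2 | 4 | yes | 57.0 | -3.2 | -2.9 | -4.8 |
| -0.2 | 7 | yes | 56.7 | -3.2 | -1.5 | -4.8 |

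Other cases:
- *Everyone perfectly stable* (both M, both hazard ratios): visit mean 55 to 60 without the discontinuation form, 54 to 59 with it. Paired change is about 0. Mixed model +0.3 to about +1 without the form, +0.2 to +0.8 with it.
- *Steep decline* (mean slope -0.6; true change about -13.8 after the floor at 0): the visit mean, without the discontinuation form, still reaches 56 with M = 6 and hazard ratio 2.7, but falls to about 48 with M = 12 and hazard ratio 1.6. The mixed model falls in every case, by roughly 6 to 12 points depending on stopping and on how discontinuation forms are placed.

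**Step 3: a second set of assumptions.** Between-patient SD 8, slope SD 0.25 per month, error SD 4, mean slope -0.25 per month (true change -0.25 x 24 = -6), median 6 or 9 months, log-hazard 0.04 or 0.08 per point, discontinuation forms omitted. Month 24 minus baseline: visit mean -0.3 to +5.6; paired change -3.4 to -4.7; mixed model -3.7 to -5.3.

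**Reading.** The visit mean rises or conceals most of the fall in nearly every case. The mixed model rises only when true change is flat or slightly negative; otherwise it falls too little. Paired change never rises beyond simulation error, but describes only the patients still assessed.

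**The case against.** The case for the plan has real weight.

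- **Change from baseline is already planned** (SAP 6.1.1). It needs both values from the same patient, so it is a within-patient, on-treatment measure close to the protocol's endpoint. This stands. A reader might infer that no planned output addresses evolution on avelumab; SAP 6.1.1 contradicts that.
- **On-treatment collection is deliberate**, and the analyses are purely descriptive (SAP 4.2). This stands too: the collection schedule is not the fault. What is missing is a statement of what each summary represents.
- **The mixed model does not turn a clear decline into a rise.** A reader might infer that it would. The calculations do not support this beyond near-flat true change.
- **Discontinuation forms catch part of the late decline.** In the tabulated scenarios they reduce the model's bias without removing it. SAP 11.1.1 does not say whether they and the progression forms enter the day windows or stay outside.
- **Numbers will be visible.** SAP 8.1.1 reports n and missing counts, so attrition will show. These do not give the baseline mean of the patients who remain.
- **The FAS label does not bias the mixed model**, because patients without forms add nothing to it. It can still distort denominators and missing counts, and it conflicts with protocol 8 and 9.7. SAP 8.2.5 marks missing data as excluded, so how those counts would appear is itself unclear.

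**Conclusion.** The point holds in limited form and is a should-fix matter of analysis and display. By-visit absolute means can rise or hide a decline through selection alone. The MAR mixed model targets a mean with no stopping or death; it can drift slightly upward near a flat course and otherwise tends to understate decline. Change from baseline is free of the upward artefact but covers only those still assessed.

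Only the direction is established. The size depends on time on drug, score variance and the link between score and stopping, none of which the documents give. The simulated values are illustrations and not forecasts for this study.

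A rise reads as improvement only under SAP 6.1.3, where higher is better. Protocol 9.4 and SAP 2.1 say higher FBISI-18 scores mean more symptoms. These statements must be reconciled before any trend is interpreted.

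**What to change.** Amend SAP 8.2.2.12 to 8.2.2.14 and 8.2.5:

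1. Beside each by-visit absolute mean, show the baseline mean of the same participants, their change from baseline, the number still on avelumab and the number of forms received.
2. Add change-from-baseline curves by time on avelumab (for example stopped before 3, 3 to 6, 6 to 12, or after 12 months), each ending at the discontinuation form. State how discontinuation and progression forms enter the windows in SAP 11.1.1.
3. Label the mixed model as a hypothetical estimate assuming no discontinuation or death. No fixed display cut-off is needed once the counts are shown.
4. Replace FAS with a PRO set of participants who initiated avelumab after study start at their site. Count a form as missing only if it was due.
5. State one score direction throughout.

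The cost is SAP wording and two extra displays from data already collected. The drawback is small strata at late visits.
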